**7.5.11 Visit 11 – EOT**

**8 Weeks Post Lead Placement: lead removal and end of treatment (EOT)**

The subject will return approximately 8 weeks after the initial lead placement. [REDACTED]

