**9.1 Primary clinical efficacy endpoint analysis**

[REDACTED]

The effectiveness of percutaneous Peripheral Nerve Stimulation (PNS) for the treatment of post-amputation pain will be assessed in the present study. The goal of the proposed [REDACTED] study is to determine if the investigational treatment produces pain relief that is clinically meaningful and greater than the placebo effect. To distinguish between the effect of the investigational treatment and the placebo effect, qualifying individuals will be randomized (1:1) to either Group #1 (Treatment) or Group #2 (Control). The groups will be identical except for whether active stimulation (Group #1) or sham stimulation (Group #2) is delivered during the first 4 weeks of the home trial. Both groups are expected to experience a similar placebo effect from the study procedures and use of the devices. In Group #1, subjects will experience both the placebo effect and the investigational treatment effect. During the sham stimulation phase in Group #2, subjects will experience only the placebo effect. Thus, if there is a difference between the mean improvements during sham stimulation and active stimulation, it can be attributed to the investigational treatment effects.

The null hypothesis ( $H_0$ ) is that the investigational treatment (Group #1, active simulation) is equal to the control (Group #2, sham stimulation) in providing pain relief. The alternative hypothesis ( $H_1$ ) is that Group #1 has a proportion of successes that is not equal to the proportion of successes of Group #2.

1.  $H_0$ : proportion of successes of Group #1 = proportion of successes of Group #2
2.  $H_1$ : proportion of successes of Group #1  $\neq$  proportion of successes of Group #2

If the proportion of successes of the investigational treatment is statistically significantly greater ( $p < 0.05$ ) than the proportion of successes of the control during the first 4 weeks of the home trial and the alternative hypothesis is accepted at the 0.05 level of significance, it will indicate that the investigational treatment is clinically significant and different than the placebo effect.

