Pain relief will be evaluated using the average pain intensity. All regions of post-amputation pain (RLP or PLP or both) that have intensities  $\geq 4$  on average during the baseline period and receive treatment with an investigational device will be used to assess the primary efficacy endpoint. All amputees will record two daily post-amputation pain scores (one daily score for RLP and one daily score for PLP) for each amputated leg in the 7-day diaries using BPI-SF Question #5. For each individual, the region(s) of post-amputation pain with a 7-day average  $\geq 4$  during baseline in a leg that receives blinded treatment from an investigational device(s) will qualify to be used in the determination of clinically-meaningful success for that subject throughout the study. Each amputee must have  $\geq 50\%$  reduction in all areas of qualifying RLP and PLP to be considered a success in the primary effectiveness endpoint analysis.

The primary endpoint of the study compares the proportion of subjects in Group #1 relative to that in Group #2 that achieve  $\geq 50\%$  reduction in all areas of qualifying post-amputation pain from baseline to the first 4 weeks of the home trial, examining the statistical superiority of proportion of clinical successes of Group #1 over the proportion of successes of Group #2. The post-amputation pain intensity scores will be determined for each subject by taking the mean of the daily average pain intensity (BPI-SF Question #5) reported in the 7-day diary at baseline compared to the mean score for the same region(s) of pain reported over the first 4 weeks of the home trial (*i.e.*, the average of all diary scores during this period). For each leg with leads, the average pain scores will only include the days when all leads are in place (e.g., if leads are placed in second leg during week 2 of home trial, then only the data from weeks 2-4 will be used). Data will be collected as described in the Schedule of Procedures (Appendix A).

**9.1.1 Baseline characteristics and changes in usage of medication affecting pain will be analyzed to determine how strong their relationships are with changes in pain intensity between baseline and EOT**

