The following variables: sex, age, baseline pain intensity, time elapsed from amputation, medications affecting pain used at baseline, prosthesis fit, baseline BDI-II score, and percent changes in usage of medication affecting pain between baseline and EOT (i.e., PRN medication usage) will be examined via a covariate analysis to determine their influence on the primary outcome.

**9.1.2 A power analysis of the 2-tailed, 2-sample Mann-Whitney test was conducted for the primary efficacy endpoint to determine the sample size for > 90% power and a 5% significance level**

A power analysis of the 2-tailed, 2-sample Mann-Whitney test was conducted with data from the previous feasibility study and data published in other studies. The proportion of successes expected for Group #1 was estimated from the previous feasibility study in which stimulation produced comfortable sensations (paresthesia) in the region of greatest pain. The proportion of successes expected for Group #2 was estimated from published studies in which sham (placebo) treatments were given to amputees with post-amputation pain. The null hypothesis that the proportion of successes of Group #1 is equal to the proportion of successes of Group #2 was tested.

[REDACTED]

[REDACTED]

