### 9.3 Secondary clinical efficacy endpoint analysis

Additional endpoints below will be assessed to document further the effectiveness of using the SPRINT Peripheral Nerve Stimulation (PNS) System for the symptomatic relief and management of post-amputation pain.

- Durability of the treatment effect on average pain intensity (Primary Endpoint) after 8-week home trial

The durability of the treatment effect on average pain intensity compares the proportion of subjects who successfully achieve  $\geq 50\%$  reduction from baseline in Group #1 at end of 8-week home trial relative to that in Group #2 at end of 4-week sham period, examining the statistical superiority of the proportion of successes of Group #1 over the proportion of successes of Group #2. The post-amputation pain intensity scores will be determined for each subject by applying the same method used for the primary endpoint: taking the mean of the daily average pain intensity (BPI-SF Question #5) reported in the 7-day diary at baseline compared to the mean score for the same region(s) of pain reported over the 8 weeks of treatment (*i.e.*, the average of all scores in the diaries during this period) for Group #1. To be

considered a success, subjects must have  $\geq 50\%$  reduction in all qualifying regions of pain, defined as regions of RLP and PLP with a baseline pain score  $\geq 4$  that received blinded treatment. The proportion of successes in Group #1 will be compared to the proportion of successes in Group #2 during the sham stimulation phase (Weeks 1-4 of the home trial). The null hypothesis is that there is no difference in success rates between the two treatment groups, versus the alternative hypothesis, that the success rates differ from one another.

- Durability of the treatment effect on average pain intensity (Primary Endpoint) at monthly intervals after start of therapy (3 - 12 months after start)

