#### 9.4 Exploratory endpoint analysis

Exploratory endpoints will be analyzed to provide information on additional outcome measures and how the system and subject characteristics affect the outcome of the investigative treatment on post-amputation pain. For all endpoints, data will be collected as described in the Schedule of Procedures (Appendix A).

- Treatment effect in Group #2  
Group #2 will receive stimulation during the second half of the home trial (Weeks 5-8), and the proportion of successes and/or mean improvements in outcome measures during this phase will be compared to those during the sham stimulation phase. In addition, a repeated measures analysis may be conducted to determine the within-subjects improvement from sham to stimulation.

Global impression of change (Patient Global Impression of Change (PGIC))

Analyses of changes in average RLP

[REDACTED]

Analyses of changes in average PLP [REDACTED]

Analyses of changes in worst RLP [REDACTED]

Analyses of changes in worst PLP [REDACTED]

[REDACTED]

- Non-opioid medication usage

[REDACTED]

- Pain Catastrophizing Scale (PCS)

[REDACTED]

- Clinician Satisfaction Survey

[REDACTED]

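### Section 9.1.1 relates medication change up to week 8 to a primary outcome that closes at week 4, and its heading and body name different outcomes

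*Combined protocol and SAP*

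**What the plan says.** The body of Section 9.1.1 states that "percent changes in usage of medication affecting pain between baseline and EOT (i.e., PRN medication usage) will be examined via a covariate analysis". The same sentence gives the purpose: the listed variables are to be "examined via a covariate analysis to determine their influence on the primary outcome". The heading of 9.1.1 gives a different target, namely "how strong their relationships are with changes in pain intensity between baseline and EOT".

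Section 9.1 defines the primary outcome as a yes/no success: at least a 50% reduction in every qualifying region. It compares the baseline diary mean with the mean score "reported over the first 4 weeks of the home trial". The planned difference between the arms is "whether active stimulation (Group #1) or sham stimulation (Group #2) is delivered during the first 4 weeks of the home trial".

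The visit schedule puts EOT at Visit 11: "8 Weeks Post Lead Placement: lead removal and end of treatment (EOT"). Table 3 agrees. Section 9.4 adds that "Group #2 will receive stimulation during the second half of the home trial (Weeks 5-8").

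Section 9.3 (Analgesic usage) has its own medication windows for opioids. One calculation uses the diary week before Visit 7 (week 4) in both arms. A second uses the diary week before Visit 11 (week 8) in Group #1, set against week 4 in Group #2.

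**The concern.** A covariate meant to explain an outcome should be measured over the period in which that outcome arises. Medication taken in weeks 5-8 cannot have influenced pain scores already recorded in weeks 1-4.

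The gap is also not neutral between arms. Group #1 is on active stimulation throughout. Group #2 is on sham while its primary outcome is recorded and on active stimulation in weeks 5-8. A medication measure taken at or up to EOT therefore reflects, in Group #2 only, a treatment condition that its primary outcome never saw.

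The two outcomes named in 9.1.1 differ in timing and in scale: responder status over weeks 1-4 in the body, change in pain intensity to EOT in the heading. Two analysts working from the visible text could fit different models. At stake is how the medication analysis can be read beside the weeks 1-4 result, which matters because Section 7.3 lets subjects use PRN medication as needed.

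**Working it through.** The plan states no overlap figure, so there is none to reproduce. The check is a day count on nominal timing.

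**Inputs**
- Primary outcome window: weeks 1-4 (Section 9.1), days 1-28.
- EOT: week 8 (Section 7.5.11), day 56.
- Group #2 on active stimulation: weeks 5-8 (Section 9.4), days 29-56.
- Week before Visit 11 (Section 9.3, opioids): days 50-56.

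**Formula.** Share inside = (medication days within days 1-28) / (all medication days).

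| Reading of 9.1.1 | Medication days | Inside days 1-28 | Group #2 medication days on active stimulation |
|---|---|---|---|
| Body, week-8 diary | 50-56 | 0/7 = 0% | 7/7 = 100% |
| Body, mean over all 8 weeks | 1-56 | 28/56 = 50% | 28/56 = 50% |

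For comparison, 0/28 = 0% of Group #2's primary-outcome days are on active stimulation. In Group #1 the share is 100% in every window.

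Two cautions apply to the table. Section 9.3 applies the week-8 opioid diary to Group #1 only; the first row extends it to both arms because 9.1.1 makes no exception for Group #2. The second row borrows a rule that Section 9.3 gives for pain, the "mean score for the same region(s) of pain reported over the 8 weeks of treatment", and no visible text applies it to medication. It is an illustration, not a bound.

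**Heading reading.** If the outcome is pain change to EOT, medication and pain can be taken over the same days and the mismatch can be zero. The outcome is then not the weeks 1-4 success defined in Section 9.1.

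**Scale.** Percent change = 100 × (F − B)/B, where B is baseline and F is follow-up PRN use. It is undefined when B = 0. The documents do not say how many subjects this would affect.

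**Check of the remedy.** Measuring medication over days 1-28 leaves 0/28 outside the outcome window. However, Section 9.1 counts pain only on days when all leads are in place, and its example is a second leg contributing weeks 2-4 (days 8-28). A fixed weeks 1-4 medication window would then leave 7/28 = 25% of its days outside. Using the same days leaves 0/21.

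**The case against.** **The heading may govern.** It names the same end point in time as the medication variable, and the plan uses its primary-endpoint label loosely: Section 9.3 attaches it to pain at 8 weeks and at later months. On that view the fault is one imprecise phrase. This stands as a possible reading. A reader might infer from the day counts that 50% to 100% of medication days are shown to lie outside the outcome window. The documents do not support that range: it assumes that the body governs, and its lower end rests on a pain-averaging rule. The conflict between heading and body remains on any reading.

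**Medication in weeks 1-4 is already analysed.** Section 9.3 compares week-4 opioid change by arm. This stands in part, so it would be wrong to infer that the plan ignores medication use in the primary window. That analysis is confined to subjects prescribed opioids at baseline and does not relate use to pain success.

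**Redacted text may add detail.** Redactions follow the introduction of the covariate analysis in Section 9.0, follow Section 9.1.2, and cover non-opioid use in Section 9.4. They might name the diary days. The 9.1.1 heading and sentence are themselves unredacted, and the conflict lies in them.

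**It is only supportive.** Agreed; this sets the weight of the point.

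**Conclusion.** The point holds as a minor defect of specification in a supportive analysis. If the body of 9.1.1 is followed, the medication measure extends into or lies wholly within weeks 5-8 while the outcome closes at week 4, and in Group #2 it brings in active-stimulation days against a sham-period outcome. With the week-8 diary applied to both arms, no medication day falls in the outcome window. If the heading is followed, the windows could match but the analysis no longer concerns the primary outcome.

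This rests on nominal visit timing and on the visible text, which does not say which diary days make up use at EOT. A reader might go further and infer that the primary comparison is biased or confounded by medication. The documents do not support that: the primary test, alpha and sample size do not depend on 9.1.1, and neither the size nor the direction of any effect on the covariate result can be derived.

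**What to change.** In Section 9.1.1:

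1. Measure PRN medication change from the baseline diary to the same home-trial diary days that enter the subject's primary outcome: weeks 1-4, or the shorter period when all leads are in place under Section 9.1. Where two legs have different periods, state which days count.
2. Make the heading and the body both name the weeks 1-4 primary outcome.
3. If an EOT analysis is also wanted, pair EOT medication change with a separately named EOT pain outcome.
4. Use one scale for all subjects, for example absolute change. Mixing percent change for some with absolute change for others would leave a coefficient that cannot be interpreted.
5. Report the result as an association. The variable arises after randomisation, so a model adjusted for it should not be presented as the treatment-effect estimate.

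The cost is a wording change to one heading and one paragraph. No new data are needed: medication is a diary item (Section 4.1), is recorded in the baseline diary (Section 7.5.1), and PRN use is entered in the diary (Section 7.3).

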#### ***Daily medications affecting pain will be permitted at levels established during baseline***

All subjects will be permitted to continue use of all medications affecting pain throughout the study; however, dosages of these medications will be controlled and recorded during the study. Subjects will be permitted to reduce or maintain their dosages of medications affecting pain but will be asked not to increase their routine dosages of these medications above the baseline dosages that were established prior to lead placement. To be eligible for participation in the study, individuals will be required to have not added new medications affecting pain [REDACTED] prior to initiating the baseline diary according to subject reported medication history.

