#### ***PRN medications will be permitted***

In addition to the medications taken regularly each day, subjects will be permitted to continue to use PRN pain medications as needed. Subjects who are not using opioids during baseline will be permitted to use any non-opioid medications as prescribed by their physician in addition to over-the-counter medications (e.g., acetaminophen, ibuprofen, etc.) as PRN medications affecting

pain as needed. Subjects who are using opioids during baseline will also be permitted to increase their use of their existing opioid as prescribed by the investigator.

Subjects will also be permitted to use over-the-counter medications as needed for pain (e.g., headache or back pain) unrelated to their post-amputation pain.

PRN medication use will be documented in the diary.

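### Section 9.1.1 announces change in medication affecting pain but defines it as PRN use only, so the covariate can miss, or give the wrong sign to, change in total analgesic use

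*Combined protocol and SAP*

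**What the plan says.** The heading of Section 9.1.1 states a broad aim: "Baseline characteristics and changes in usage of medication affecting pain will be analyzed to determine how strong their relationships are with changes in pain intensity". It carries no restriction to PRN drug. The paragraph beneath lists eight variables, the last being "percent changes in usage of medication affecting pain between baseline and EOT (i.e., PRN medication usage", and says that they "will be examined via a covariate analysis to determine their influence on the primary outcome".

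Section 7.3 separates the two kinds of use. For daily medication: "Subjects will be permitted to reduce or maintain their dosages of medications affecting pain but will be asked not to increase their routine dosages". For as-needed medication: "In addition to the medications taken regularly each day, subjects will be permitted to continue to use PRN pain medications as needed". Under the same PRN heading, "Subjects who are using opioids during baseline will also be permitted to increase their use of their existing opioid as prescribed by the investigator".

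Section 7.3 also has doses and pain interventions recorded in the CRF and diaries. Section 9.1 bases the primary outcome on diary scores averaged over weeks 1 to 4 of the home trial. EOT is the week 8 visit (Section 7.5.11), and Group #2 receives active stimulation in weeks 5 to 8 (Section 9.4).

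**The concern.** The abbreviation i.e. equates total medication change with PRN change. Section 7.3 does not: PRN drug comes on top of daily drug, and daily drug is allowed to fall. A programmer who follows Section 9.1.1 as written would leave out the routine component altogether.

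This is the only visible analysis that relates medication change to the primary pain result. If a subject cuts routine drug and the covariate records no change, or an increase, the estimated relation between analgesic change and pain can be weakened or take the wrong sign. The report's statement on how far medication influenced the primary outcome would then rest on a variable that does not measure what its name says.

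**Working it through.** The documents give no figure for this covariate, so there is none to reproduce. The check is of the definition. All dose units below are assumed, and routine and PRN drug are expressed on one common scale.

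**Formulas.** Let R0 and P0 be routine and PRN use at baseline, and R1 and P1 the later values.

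- Section 9.1.1 as written: 100 × (P1 − P0) / P0
- Total use: 100 × [(R1 + P1) − (R0 + P0)] / (R0 + P0)

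**Illustrative records (routine + PRN).**

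| Baseline | Later | PRN only | Total |
|---|---|---|---|
| 40 + 10 | 20 + 10 | 0/10 = 0% | −20/50 = −40% |
| 40 + 10 | 20 + 15 | +5/10 = +50% | −15/50 = −30% |
| 40 + 10 | 20 + 30 | +20/10 = +200% | 0/50 = 0% |
| 40 + 10 | 40 + 5 | −5/10 = −50% | −5/50 = −10% |
| 40 + 0 | 20 + 0 | 0/0, undefined | −20/40 = −50% |
| 40 + 0 | 20 + 10 | 10/0, undefined | −10/40 = −25% |
| 60 + 10 | 30 + 5 | −5/10 = −50% | −35/70 = −50% |

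**When the two measures differ.** Let s = R0/(R0 + P0) be the routine share of baseline use, r the percent change in routine use and p the percent change in PRN use. Then total change = s·r + (1 − s)·p, and PRN-only change minus total change = s·(p − r). The gap is zero if s = 0 (no routine drug) or if p = r (both components change by the same proportion, including no change in either). The last row of the table is a case of p = r.

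**Range over the unknown share.** The documents do not give s, so take 20% to 90% and halve routine use (r = −50).

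- PRN unchanged (p = 0): PRN-only is 0%; total is −50s, from −10% (s = 20%) to −45% (s = 90%).
- PRN up by half (p = +50): PRN-only is +50%; total is 50 × (1 − 2s), giving +30% at s = 20%, 0% at s = 50% and −40% at s = 90%. In this scenario the sign is reversed only when routine drug is more than half of baseline use.

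**Time window.** The covariate runs from baseline to week 8, while the primary outcome covers weeks 1 to 4. In Group #2, change measured at EOT includes up to four weeks of active stimulation after the outcome window has closed. The heading of 9.1.1 also speaks of pain change to EOT, but its paragraph names the primary outcome as the target, and the windows do not match for that target.

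**The case against.** The best defence is that PRN is the component left free to rise. Subjects are asked not to raise routine doses, so extra analgesia that could imitate a device effect should appear mainly as PRN use. A routine cut would, if anything, work against showing pain relief. This is a fair reason to report PRN change, and it stands to that extent. It does not justify naming PRN change as total change, because routine use may still fall and the stated aim is to relate medication change to pain.

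Second, routine opioid change is not lost from the plan. Section 9.3 compares mean daily morphine-equivalent dose between groups at week 4, and Group #1 at week 8 with Group #2 at week 4, in subjects prescribed opioids at baseline. Nothing visible limits that to PRN drug. A reader might infer that routine reductions go unexamined altogether; the documents do not support that. What Section 9.3 does not do is relate the change to the primary outcome, and it omits subjects without baseline opioids. The non-opioid method in Section 9.4 is redacted and cannot be judged.

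Third, i.e. may be a slip for e.g. or for including. If so, the text still needs correcting, since as written it restricts the variable.

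**Conclusion.** The point holds as a defect of definition in a supportive analysis. With baseline PRN use above zero, a routine cut with PRN unchanged scores 0%. A routine cut partly replaced by PRN can score as an increase while total use falls. With zero baseline PRN use the value is undefined. The size depends on the routine share of baseline use, which the documents do not give; the figures above are illustrations, not estimates.

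Three stronger readings go too far:

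- A reader might infer that PRN-only change is wrong for everyone who takes routine drug. It is not: it agrees with total change whenever both components change in proportion.
- A reader might infer that the error differs between arms. It is plausible that subjects with less pain cut routine doses more, but no passage gives reduction rates by response or by arm. By EOT both groups have received active stimulation, which weakens the argument further.
- A reader might infer that the primary result is at risk. The primary test, the success definition and the sample size do not use this variable.

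**What to change.** In Section 9.1.1:

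1. Delete the parenthesis that equates medication change with PRN usage.
2. Derive the covariate from routine plus PRN use together: total daily morphine-equivalent dose for opioids, and for non-opioids a separate category of increase, no change or decrease. State in advance how a subject whose non-opioid drugs move in opposite directions is coded.
3. Measure the change over weeks 1 to 4, to match the primary outcome. If change to EOT is also wanted, report it separately and note that Group #2 is then on active stimulation.
4. Where baseline use is zero, use absolute change or a category instead of percent change.
5. Report the PRN and routine components descriptively, which keeps the information that the present definition was meant to give.

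The cost is a wording change and one or two more derived variables. Section 7.3 already calls for the doses to be recorded, and Section 9.3 already uses morphine-equivalent dose from the diary. Retitling the section as PRN only would remove the contradiction, but would leave routine change unrelated to the primary outcome.

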- Depression (Beck Depression Inventory (BDI-II)) at monthly intervals after start of therapy

The analysis of treatment effect on depression examines the statistical superiority of the mean percent improvement from baseline at monthly intervals of Group #1 relative to that of Group #2. In Group #1, the baseline BDI-II score (assessed at Visit 1) will be compared to the BDI-II score at each monthly interval after start of therapy. In Group #2, the baseline BDI-II score will be compared to the score at the end of the 4-week sham period. The null hypothesis is that there is no difference in mean percent improvement between the two treatment groups (*i.e.*, Group #1 at the monthly interval vs. Group #2 at end of sham period), versus the alternative hypothesis, that the mean percent improvements differ from one another. Testing will be conducted at the 0.05 level of significance.

- Analgesic usage

The analysis of treatment effect on analgesic usage will evaluate the change in opioid analgesic usage separately from the change in non-opioid analgesic usage (see Exploratory Measures, Section 9.4).

Changes in opioid analgesic usage will be calculated using morphine equivalent dosing (MED) to compare the mean percent change from baseline to the end of first 4 weeks in Group #1 relative to that of Group #2. Analysis will be conducted to determine if the mean change of Group #1 is statistically significantly greater than the mean improvement of the Group #2. The change in the opioid analgesic usage will be determined for subjects (who are receiving prescribed opioid medications at baseline) by taking the mean of the daily MED for the entries reported in the 7-day diary at baseline compared to the mean of the daily MED for the entries reported in the 7-day diary during the week before Visit 7 (*i.e.*, week 4 of home trial). The null hypothesis is that the mean change in MED is not significantly different in both groups, and the alternative hypothesis is that the mean change for the two groups differ.

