The change in MED at the end of the 8-week home trial will also be calculated. For Group #1, the change in the opioid analgesic usage will be determined for subjects (who are receiving prescribed opioid medications at baseline) by taking the mean of the daily MED for the entries reported in the 7-day diary at baseline compared to the mean of the daily MED for the entries reported in the 7-day diary during the week before Visit 11 (*i.e.*, week 8 of home trial). This will be compared to the mean change in MED during week 4 of the home trial in Group #2 (*i.e.*, final week of the sham period), as calculated in the

previous analysis. The null hypothesis is that the mean change in MED is not significantly different in both groups, and the alternative hypothesis is that the mean change for the two groups differ.

- Prosthetic usage (hours of daily prosthetic usage recorded in diary) at end of first 4 weeks and after 8-week home trial
- The analysis of treatment effect on the prosthetic usage compares the mean rank scores (of 25 possible ranks, ranging from 0 to 24 hours) at baseline to the end of first 4 weeks and after the 8-week home trial of Group #1 relative to that of Group #2, examining the statistical superiority of the mean rank scores of Group #1 over that of Group #2. The mean rank scores will be determined for each subject by taking the 7-day mean of the daily hours of prosthetic usage reported in the 7-day diary at baseline (for the residual limb with the region of pain being used for primary efficacy) compared to the 7-day mean of the daily hours of prosthetic usage reported in the diary during the week before Visit 7 and the last week of stimulation before the end of the 8-week home trial. The null hypothesis is that the mean rank scores for both groups are not significantly different. The alternative hypothesis is that the mean ranks scores for the two groups differ.
- Subject Satisfaction Survey  
A survey will be administered to the subjects at EOT to assess their satisfaction with the study and device.

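### Section 9.1.1 relates PRN medication change up to EOT (week 8) to a primary outcome that covers weeks 1-4, so the covariate runs past the outcome window and past Group #2's switch to active stimulation

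*Combined protocol and SAP*

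**What the plan says.** The body of Section 9.1.1 lists eight variables to be examined for their influence on the primary outcome. Seven are fixed at baseline: sex, age, pain intensity, time since amputation, pain medications, prosthesis fit and BDI-II. The eighth arises after randomisation: "percent changes in usage of medication affecting pain between baseline and EOT (i.e., PRN medication usage) will be examined via a covariate analysis". The heading of the same section describes the aim differently, as determining "how strong their relationships are with changes in pain intensity between baseline and EOT".

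Section 9.1 defines success as at least a 50% "reduction in all areas of qualifying post-amputation pain from baseline to the first 4 weeks of the home trial", using the average of all diary scores in that period. Section 7.5.11 places EOT at Visit 11: "8 Weeks Post Lead Placement: lead removal and end of treatment (EOT)". Section 9.1 gives sham to Group #2 in the first 4 weeks, and Section 9.4 states that "Group #2 will receive stimulation during the second half of the home trial (Weeks 5-8)".

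For opioids, Section 9.3 compares the arms in subjects on prescribed opioids at baseline, using "entries reported in the 7-day diary during the week before Visit 7". It adds an 8-week version based on "entries reported in the 7-day diary during the week before Visit 11". It says that the analysis "will evaluate the change in opioid analgesic usage separately from the change in non-opioid analgesic usage". The non-opioid analysis is in Section 9.4, where its detail is redacted.

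**The concern.** A covariate meant to help explain an outcome should be measured before or during the outcome window. Here the medication change is carried to week 8, while the outcome closes at week 4. Between those times Group #2 changes treatment. If its PRN use falls once stimulation starts, the EOT value no longer reflects use under sham.

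PRN use matters because it is the flexible part of the medication rules in Section 7.3. Routine doses are not to rise above baseline, but PRN use is allowed, and baseline opioid users may increase their existing opioid as the investigator prescribes. Different analgesic use between arms could contribute to a pain difference or mask one. Section 9.1.1 is the visible analysis that links medication change to the primary outcome, so its window should be the blinded one.

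The heading and body also name different outcomes, so the analyst must choose between them.

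**Working it through.** **Windows side by side**

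| Item | Window | Source |
|---|---|---|
| Primary outcome | Baseline week vs weeks 1-4 (28 days) | 9.1 |
| Sham vs active contrast | Weeks 1-4 | 9.1 |
| Group #2 on active stimulation | Weeks 5-8 | 9.4 |
| EOT | Visit 11, week 8 | 7.5.11 |
| PRN covariate | Baseline to EOT | 9.1.1 body |
| Outcome in heading | Pain change, baseline to EOT | 9.1.1 heading |
| Opioid dose, first comparison | Week before Visit 7 (week 4) | 9.3 |

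**Overlap with the outcome window.** The visible text does not say how EOT use is summarised. There are two natural readings.
- Week before Visit 11, as Section 9.3 does for opioid dose: 0 of 7 days lie in the 28-day outcome window, and all 7 follow the switch.
- Average over the 8-week home trial: 28 of 56 days (50%) follow the switch.

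**Which outcome is meant.** Under the body, the windows do not match. Under the heading they match, but both arms are on active stimulation by EOT, so the analysis no longer bears on the sham-controlled contrast. Either way the text needs correcting.

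**Illustration under assumed rates.** The documents give no PRN rates. Assume 27 subjects per arm (Section 6.2), Poisson doses, a gamma between-subject CV of 0.5, and mean use of 0.3, 1 or 2 doses per day. Group #1 is stable. Group #2 rises 30% in weeks 1-4 and keeps a fraction f of that rise in weeks 5-8. The test is a two-sided t-test at 0.05 on absolute change from a 7-day baseline, with 10,000 runs. The table gives the approximate percentage of runs that detect the rise at 0.3 / 1 / 2 doses per day.

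| Measure | f = 0 | f = 0.5 | f = 1 |
|---|---|---|---|
| Weeks 1-4 (28 days) | 28 / 70 / 93 | same | same |
| Week 4 only (7 days) | 19 / 48 / 77 | same | same |
| Week 8 only (7 days) | 5 / 5 / 5 | 8 / 16 / 28 | 19 / 48 / 77 |
| Average of 8 weeks | 11 / 27 / 47 | 19 / 50 / 79 | 31 / 75 / 95 |

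This is a comparison of arms, which Section 9.1.1 does not specify, so the table does not measure error in the planned covariate analysis. It shows only that the information lost depends on the summary and on persistence. The fair comparison for week 8 is week 4, also 7 days. The loss there is total if nothing persists and nil if everything does.

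**Percent change.** It is undefined when baseline use is zero. Under the same model, P(zero in 7 days) = (1 + 7 × rate / 4)^-4, which is 18.5%, 1.7% and 0.2% at the three rates. Multiplied by 54 subjects, that is about 10, 0.9 and 0.1. Among stable users with non-zero baseline, a week-8 change of 50% or more in either direction arises by chance in about 65%, 41% and 25%.

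**Why not adjust for it.** A linear illustration assumed a true weeks 1-4 effect of -1 and medication that follows current pain with slope 0.3 to 1.0. Adjusting for the weeks 1-4 medication change shrank the estimated effect to between -0.84 and -0.34. A correctly timed covariate is still affected by treatment.

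**The case against.** The strongest reply is that the heading gives a coherent reading: pain change and medication change both run from baseline to EOT, and the phrase about the primary outcome is merely loose. Section 9.3 does have an 8-week pain analysis for Group #1, which is stimulated throughout. This may be what was intended. It makes the repair largely editorial but does not remove it, because the body still names the primary outcome, and in Group #2 the EOT window mixes sham and active periods.

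Second, opioid use is already handled in the right window. Section 7.3 allows opioid increases for subjects using opioids at baseline, and Section 9.3 compares opioid dose between arms at week 4 in essentially that group. This stands. It narrows the gap to PRN use, especially non-opioid use, and to the link between medication and success, which the Section 9.3 comparison does not examine. The window of the non-opioid analysis in Section 9.4 is redacted and cannot be judged.

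Third, a reader might infer that the EOT covariate says nothing about weeks 1-4. That is too strong: with 8-week averaging and full persistence, it does no worse than weeks 1-4 in the illustration.

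Fourth, a reader might infer that the mistimed covariate would lead people to believe that medication use was similar between arms under blinding. Section 9.1.1 is not a comparison of medication between arms, so that does not follow from it.

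**Conclusion.** The mismatch is in visible, current text and is not a product of redaction. The covariate includes, or consists entirely of, time after the outcome window closes and after Group #2 leaves sham, and the heading contradicts the body. The analysis therefore cannot reliably show how PRN use in the blinded period relates to the primary result.

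The consequence is minor. It touches one of eight covariates in a supportive analysis. A reader might infer that the primary comparison is compromised, but no visible text adjusts the primary test for this variable, so the documents do not support that. Nor do they support saying that the plan lacks a medication analysis in the blinded window, given the week-4 opioid comparison and the redacted Section 9.4 text.

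The timing point rests on no assumed number. The size of the loss does: PRN rates, the 30% rise and its persistence are all assumptions. The percent-change problem is secondary and matters mainly if PRN use is light.

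**What to change.** In the heading and body of Section 9.1.1, end the medication and pain windows with the first 4 weeks of the home trial instead of EOT. If the visit schedule (not visible) limits diary medication entries to certain weeks, use the week before Visit 7, as Section 9.3 does. The shorter window costs some precision.

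Report the PRN change by arm and by success status, labelled descriptive or exploratory. Do not use it to adjust the treatment effect, because it arises after randomisation. If a relation at EOT is also wanted, present it as a separate 8-week analysis. Absolute change, such as PRN doses or days per week, is advisable in place of percent change so that subjects with no baseline PRN use are kept.

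The cost is one reworded heading and sentence, best settled before unblinding. Sections 4.1 and 7.3 show that the diary already records pain medication and PRN use, so no new field should be needed. Over-the-counter drugs taken for unrelated pain will add some noise unless the diary separates them. The primary analysis does not change.
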